Study Protocol

Human Immune Responses to Yellow Fever Vaccination

Protocol Date: February 15, 2023

NCT00694655

Human Immune Responses to Yellow Fever Vaccination

(YF Immune Response)

Principal Investigator: [name], MPH

Hope Clinic of Emory University
Decatur, GA 30030

Funding: NIH, NIAID, Cooperative Centers for Human Immunology,
(2U19AI057266-16, PI: [name])

**Co-Investigators at
Emory Vaccine Center:** [name]

[name]
[name]

**External Laboratory
Collaborators:**

[name]
Associate Professor, Division of Vaccine Discovery
La Jolla Institute for Allergy & Immunology (LIAI)

[name]
Professor of Microbiology and Immunology
Stanford University

TABLE OF CONTENTS

	Page
1	Background Information and Scientific Rationale 4
1.1	Background Information 4
1.2	Rationale for including non-travelers and travelers 6
1.3	Scientific Rationale 7
1.4	Potential Risks and Benefits 8
2	Objectives 9
3	Study Design 9
4	Study Enrollment 10
4.1	Subject Inclusion Criteria 10
4.2	Subject Exclusion Criteria 10
4.3	Randomization Procedures 11
5	Study Intervention 11
5.1	Study Product Description 11
5.2	Dosage, Preparation and Administration of Study Product 11
5.3	Accountability Procedures for the Study Vaccine 12
6	Study Procedures 12
6.1	Screening Visit 12
6.2	Pre-Vaccination Visit 12
6.3	Enrollment/Vaccination Visit (Day 0) 12
6.4	Leukapheresis Procedure 13
6.5	Follow-up Visits 13
6.6	Final Study Visit 14
7	Safety Assessment 15
7.1	Adverse Events and Serious Adverse Events 15
7.2	Assessment of Severity of Adverse Events 16
7.3	Relationship to Study Intervention 17
8	Laboratory 18
8.1	Laboratory Assays or Procedures 18
8.2	Specimen Preparation, Handling, and Shipping 20
9	Statistical Considerations 20
10	Source Documents and Access to Source Data/Documents 20
11	Quality Control and Quality Assurance 20
12	Ethics/Protection of Human Subjects 20
13	Data handling and Record Keeping 21
14	Publication Policy 21
15	Literature References 21
16	Appendices 23

PROTOCOL SUMMARY

Title: YFV Immune Responses: Human Immune responses to Yellow Fever Vaccination

Population: Healthy males and females between 18 to 45 years of age

Number of sites: 1

Study Duration: 5 years

Number of subjects: 250 adults, ages 18-45. We may need to screen up to 1000 adults to enroll a total of 250 participants due to screen failures)

Subject Participation Duration: 12 months

Description of Intervention: YF-17D (YF-VAX®;Yellow Fever Vaccine)

Objectives:

Primary:

1. Isolation and characterization of yellow fever vaccine-specific adaptive immune responses: characterize the magnitude and quality of yellow fever virus-specific T cell responses, antibody secreting cells and memory B cells.
2. Determine the signatures of innate immune responses: cytokines, chemokines, dendritic cells and microarray analyses on peripheral blood mononuclear cells.

Secondary:

1. Compare the magnitude and kinetics of T and B cell responses, antibody secreting cells and memory B cells at various timepoints.
2. Isolation and characterization, and phenotypic analysis of Epstein-Barr virus, cytomegalovirus and yellow fever virus-specific CD8 T cells.

Description of Study Design:

Healthy adults (18-45 years of age) with no previous vaccination history for flaviviruses and no contraindications will be vaccinated using YF-17D. Serial blood specimens will be collected from participants up to 1 year after YF-17D administration. Peripheral blood mononuclear cell isolation and sorting of yellow fever virus tetramer-specific population will be performed. Subsets of participants will undergo leukapheresis and lymph node fine needle aspirates.

1 BACKGROUND INFORMATION AND SCIENTIFIC RATIONALE

1.1 Background Information

Yellow fever (YF) is a viral disease that is transmitted to humans through the bite of an infected mosquito. Yellow fever is a life-threatening infection that can result in hepatitis, renal failure and coagulation abnormalities, and in severe cases, death¹. Yellow fever was a major public health threat in the colonial United States in the 18th and 19th centuries.

Yellow fever is endemic in over 40 countries, and approximately 125 countries require proof of vaccination for entry by travelers at risk. An estimated 200,000 cases of yellow fever occur annually in South America and Africa, making it an important vaccine-preventable disease among travelers to endemic areas². Yellow fever can be prevented by vaccination with the Yellow Fever Vaccine, YF-VAX[®] (made from the 17D strain of YFV). Currently, the Centers for Disease Control and Prevention (CDC) and World Health Organization (WHO) recommend the Yellow Fever Vaccine for people aged 9 months to 59 years who are traveling to or living in a yellow fever endemic area².

Many flaviviruses, including yellow fever virus (YFV), dengue virus (DEN), West Nile virus, Japanese encephalitis virus and tick-borne encephalitis (TBE) virus are important human pathogens. Many flaviviruses are transmitted by hematophagous arthropods (mosquitoes and ticks). Indeed, dengue, yellow fever, the TBE virus complex and Japanese encephalitis globally represent the most important mosquito-borne diseases causing extensive morbidity and mortality around the world¹. Even within the United States (US), the dramatic spread of West Nile virus infection over the past few years has provided both the public and public health authorities with a vivid example of the present (and potential future) threats posed by emerging zoonotic infections.

A very interesting, but unexplained aspect of flavivirus biology is how infection with different members of the same virus family can lead to such diverse types of host-virus interactions and variable disease outcomes. For example, YFV infection can be fatal, but if the infected host survives, long-term protective immunity is seen^{1, 3, 4}. Alternatively, DEN causes an acute infection with associated acute disease manifestations. However, more severe disease outcomes are observed following secondary infection with a distinct serologic type of DEN^{1, 3}. Understanding why the human immune system can successfully contain one flavivirus infection, but not another is both a fascinating scientific enigma in human immunology and a topic with substantial practical importance to public health. Given the great global public health threats posed by epidemic and emerging flavivirus infections, and the need to define the biological basis of successful induction and maintenance of protective immunity by vaccination, elucidation of the immunologic mechanisms underlying the generation and maintenance of protective immunity to the Yellow Fever Vaccine should be extremely useful. Furthermore, definition of the attributes of such a highly effective vaccine should help expedite the development and evaluation of new and/or improved vaccines to prevent important prevalent and emerging infectious diseases.

YF-17D is considered to be one of the safest and most effective viral vaccines ever developed. This vaccine is known to stimulate broad-spectrum immune responses, including cytotoxic T cells, and Th1 and Th2 responses, as well as neutralizing antibody titers that can persist for up to 30 years, after a single vaccination^{5, 6}. Despite the great success of this empiric vaccine,

there has been relatively little understanding of the mechanisms by which YF-17D induces such robust protective immune responses. In our past and current U19 grant we have begun to elucidate the innate and adaptive signatures induced by YF-17D in healthy adults between the ages of 18 and 45^{7,8} and T cell memory responses⁹⁻¹².

We hope to apply the best contemporary methods in immunology, genomics, and proteomics to characterize in detail a successful immune response to YF-17D. This characterization should identify new immunologic predictors that could serve as surrogates for future vaccine efficacy studies. In addition, these findings could guide development of a safer yellow fever vaccine (or the derivation of safer alternative vaccination regimens using the currently available vaccine).

The goal of this study is to use the live attenuated Yellow Fever Vaccine (YF-VAX[®], Sanofi-Pasteur) as a safe and effective model for viral infection to understand human immune response to viral antigens. Yellow fever virus vaccine is the viral infection model that we have chosen for the following reasons:

- The yellow fever live, attenuated 17D vaccine strain is one of the most efficacious vaccines available and has been in use since the 1930s.
- Since most of the US population is not exposed to YFV, immunization of adult participants with the 17D vaccine strain allows for examination of the innate immunity and the naïve T and B cell response in humans during primary infection and the subsequent development of memory T cells after resolution of the primary infection.
- YF-17D vaccination induces long-term immunity that lasts for decades. By studying how the human immune system responds to an effective vaccine such as the Yellow Fever Vaccine, we hope to learn more about the normal functioning of the immune system so that it might be possible to design new, more effective vaccines to prevent important infectious diseases. Therefore, this vaccine can serve as an ideal model to help us decipher the properties that make a vaccine effective.
- YF-17D vaccination leads to limited infection without causing the disease.

1.2 Rationale for including non-travelers and travelers

The Yellow Fever Vaccine (YF-17D; YF-VAX[®]) is a live, attenuated vaccine that has been used for prevention of yellow fever since 1937 with over 500 million doses administered². There is no treatment available for yellow fever and the only yellow fever vaccine currently licensed for use in the US is YF-VAX[®], manufactured by Sanofi Pasteur (Swiftwater, Pennsylvania). According to the Advisory Committee on Immunization Practices (ACIP) guidelines, the Yellow Fever Vaccine is recommended for persons who are aged 9 months and older who are traveling to or living in areas at risk for YFV activity or traveling to a country with an entry requirement for vaccination. In some cases, people younger than 9 months who are at increased risk may receive the yellow fever vaccine. Laboratory personnel who might be exposed to yellow fever virus or vaccine virus may also need YF-VAX[®]¹³. We plan to enroll adults between 18 to 45 years of age, who are traveling to yellow fever endemic areas, laboratory workers and also those who don't have imminent travel plans.

The Yellow Fever Vaccine is a safe and effective vaccine. Adverse events (AEs) seen with YF-17D are typically mild and may include headache, myalgias, low-grade fever and discomfort at the injection site. These mild AEs occur in about 25% of vaccinees¹³. There have been rare reports of severe AEs. Specifically, the yellow fever vaccine associated neurotropic disease

(YF-AND), and yellow fever vaccine-associated viscerotropic disease (YF-AVD). YF-AND may include post-vaccinal encephalitis, Guillain–Barré syndrome, and autoimmune disease with central or peripheral nervous system involvement. YF-AVD is a disease that clinically resembles naturally acquired infection and may include a spectrum of disease severity, from moderate illness with focal organ dysfunction to severe disease with overt multiple organ system failure and death. The risk factors for YF-AVD are advanced age and thymus dysfunction^{2, 5, 6, 13}.

AEs seen with administration of the Yellow Fever Vaccine are noted on the Yellow Fever Vaccine Information Sheet (VIS) published by the CDC. All participants will be required to read the most current VIS prior to being vaccinated (<https://www.cdc.gov/vaccines/hcp/vis/vis-statements/yf.html>). A review of AEs reported to the U.S. Vaccine Adverse Event Reporting System (VAERS) from 2000 to 2006 was published by the CDC². It showed that the overall reporting rate (for all ages) for anaphylaxis was 1.8 per 100,000 doses. YF-AND was 0.8 per 100,000 doses and YF-AVD was 0.4 per 100,000 doses. The reporting rates were higher for vaccinees aged \geq 60 years – 1.8 and 1.4 per 100,000 doses for YF-AND and YF-AVD, respectively. In general, all AEs were higher in males than females. Based on the above data, and discussions with the Yellow Fever Vaccine experts at the CDC, we feel that the overall risk of a serious adverse event (SAE) for participants we plan to recruit between 18 to 45 years old will be low (0.4 to 0.8 cases per 100,000 doses).

This study plans to recruit both travelers and non-travelers to yellow fever endemic areas for participation. International travel has been severely restricted in the US due to the COVID-19 pandemic which began in January 2020 and remains ongoing, significantly shrinking the pool of potential traveler participants. We are restricting the maximum age of our participants to 45 years (age cut off by the CDC is 59 years) and we plan to select healthy adults who meet the inclusion/exclusion criteria to minimize any potential yellow fever vaccine-related SAEs (see section 4). To meet the planned enrollment goals of this study (funded via the NIH U19 grant mechanism), we need to be inclusive of both travelers and non-travelers. It is also worth noting that colleagues at other universities who conduct similar studies—since the Yellow Fever Vaccine is a model vaccine—use the approach of including non-travelers. Much of the recruitment will still focus on travelers since they will have the greatest interest in participation.

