1.4 Potential Risks and Benefits

1.4.1 Potential Risks

YF-VAX® is an FDA approved vaccine that is routinely recommended for persons 9 months of age or older who are traveling or living in a country where yellow fever is endemic. However, there are some risks associated with YF-VAX®. Mild reactions include soreness, redness, and swelling at the injection site, mild headache, muscle aches and mild fever and in up to 25% of the vaccines 5 to 10 days after vaccination. Severe reactions to the vaccine have been reported but are extremely rare. (Please refer to the Vaccine Information Sheet and Section 1.2).

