4.2 Subject Exclusion Criteria

1. Prior receipt of a yellow fever vaccine
2. Lived in a country/area which is endemic for yellow fever
3. Travel to country/area which is endemic for yellow fever. Subject to investigator discretion
4. History of previous yellow fever, West Nile, Dengue, St. Louis encephalitis, Japanese encephalitis vaccination or infection
5. Any history of allergy to eggs, chicken or gelatin or to any previous vaccine
6. A history of a medical condition resulting in impaired immunity (such as HIV infection, cancer, particularly leukemia, lymphoma, use of immunosuppressive or antineoplastic drugs or X-ray treatment). Persons with previous skin cancers or cured non-lymphatic tumors are not excluded from the study
7. History of HIV infection
8. Active Hepatitis B or Hepatitis C infection
9. COVID-19 infection in the last 30 days. Symptoms of COVID-19 must be completely resolved before yellow fever vaccine receipt.
10. History of any chronic medical conditions that are considered progressive (ex, diabetes, heart disease, lung disease, liver disease, kidney disease, gastrointestinal diseases and uncontrolled hypertension). Use of systemic immunosuppressive medications (ex, prednisone) for 2 weeks or more in the past 3 months
11. History of excessive alcohol consumption, drug abuse, psychiatric conditions, social conditions or occupational conditions that in the opinion of the investigator would preclude compliance with the trial
12. Thymus gland problems (such as myasthenia gravis, DiGeorge syndrome, thymoma) or removal of thymus gland or history of autoimmune disorder

13. Recipient of a blood products or immune globulin product within 42 days of the vaccination visit. Participants who received COVID mAbs for treatment are not excluded
14. Pregnant women and nursing mothers or women who are planning to become pregnant for the duration of the study
15. Any condition in the opinion of the investigator that would interfere with the proper conduct of the trial

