6.2 Enrollment/Vaccination Visit (Day 0)

This visit will serve as an enrollment and vaccination visit for all participants. This visit may occur on the same day as the Screening Visit if the participant's HLA type is known prior to Screening. At this visit, the following activities may be performed:

- Physical exam
- Vital signs
- Collection of current medications
- Blood sample collection
- Urine pregnancy test (for women of childbearing potential)
- AE collection (any AE present prior to vaccination will be considered medical history)
- Vaccine administration
- Reactogenicity symptom diary distribution

Prior to vaccine administration, participants will be asked to read the Vaccine Information Sheet for the Yellow Fever Vaccine per CDC guidelines. After vaccination, participants will be observed for a minimum of 20 minutes for any immediate hypersensitivity reactions and will be given the International Certificate of Vaccination.

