7 SAFETY ASSESSMENT

7.1 Adverse Events and Serious Adverse Events

An adverse event (AE) is any untoward medical occurrence in a clinical investigation subject administered a pharmaceutical product regardless of its causal relationship to the study treatment. An AE can therefore be any unfavorable and unintended sign (including an abnormal laboratory finding), symptom or disease temporally associated with the use of a medicinal (investigational) product.

Any medical condition that is present at the time that the subject is screened will be considered as baseline and not reported as an AE. However, if the severity of any pre-existing medical condition increases, it will be recorded as an AE. The start and stop date of each reported AE will be recorded on the appropriate CRF. AEs characterized as intermittent require documentation of onset and duration of each episode.

AEs occurring during the trial-collection and reporting period will be documented appropriately regardless of relationship to study product. At each study visit, the investigator will inquire about the occurrence of AE/SAEs since the last visit. AEs will be followed through resolution.

A summary report of all AEs will be reviewed at regularly scheduled quarterly meetings by the study team.

Serious Adverse Event (SAE): An AE or suspected adverse reaction is considered “serious” if, in the view of either the Principal Investigator (PI) or appropriate sub-investigator, it results in any of the following outcomes:

- Death,
- A life-threatening AE*,
- Inpatient hospitalization or prolongation of existing hospitalization,
- A persistent or significant incapacity or substantial disruption of the ability to conduct normal life functions, or
- A congenital anomaly/birth defect.
- Important medical events that may not result in death, be life-threatening, or require hospitalizations may be considered serious when, based upon appropriate medical judgment they may jeopardize the patient or subject and may require medical or surgical intervention to prevent one of the outcomes listed in this definition. Examples of such medical events include allergic bronchospasm requiring intensive treatment in an emergency room or at home, blood dyscrasias or convulsions that do not result in inpatient hospitalization, or the development of drug dependency or drug abuse.

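### Does the quoted overall SAE risk at ages 18–45, 0.4 to 0.8 per 100,000 doses, have to be corrected?

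*Combined protocol and SAP*

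**What the plan says.** The statement is in section 1.2 of the protocol, which argues for enrolling people without imminent travel plans as well as travelers. The section introduces severe events with two syndromes in mind: "There have been rare reports of severe AEs. Specifically, the yellow fever vaccine associated neurotropic disease" (YF-AND) and, next to it, viscerotropic disease (YF-AVD). It then reports rates from a review of passive VAERS reports for 2000 to 2006, described as covering all ages: "anaphylaxis was 1.8 per 100,000 doses. YF-AND was 0.8 per 100,000 doses and YF-AVD was 0.4 per 100,000 doses". For vaccinees aged 60 and over it gives "1.8 and 1.4 per 100,000 doses for YF-AND and YF-AVD, respectively".

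Citing these data and discussions with CDC experts, the authors say they feel that the overall SAE risk for the people they plan to "recruit between 18 to 45 years old will be low (0.4 to 0.8 cases per 100,000 doses"). No rate for ages 18–45 or for under 60 is given, and no calculation is shown.

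Other places bear on the point. Section 1.4.1 says "Severe reactions to the vaccine have been reported but are extremely rare" and sends the reader to the Vaccine Information Sheet and to section 1.2. Section 4.2 excludes people with "Any history of allergy to eggs, chicken or gelatin or to any previous vaccine". Section 6.2 has participants "observed for a minimum of 20 minutes for any immediate hypersensitivity reactions". Among important medical events that may be judged serious, section 7.1 says: "Examples of such medical events include allergic bronchospasm requiring intensive treatment in an emergency room or at home".

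**The concern.** Three features make the sentence look like an error.

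- The ends of the range equal the listed YF-AVD and YF-AND rates. Rates of two different events are not the lower and upper limits of one total; an overall risk would add them.
- Anaphylaxis has the largest all-age rate in the list and is not in the range. No reason is given, although a severe allergic reaction can be an SAE under section 7.1.
- The figure is offered for ages 18–45, yet the only rates shown are for all ages or for age 60 and over.

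This is the only numerical overall SAE risk in the protocol. It helps to justify vaccinating people who may have no travel need for the vaccine, and section 1.4.1 points back to it. An ethics committee could take it as a total for this age group, which the listed data do not show. If it were too low by enough to matter, the balance of risk and benefit would have been put too favourably.

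**Working it through.** **Inputs.** From section 1.2, per 100,000 doses: anaphylaxis 1.8, YF-AND 0.8 and YF-AVD 0.4 (all ages); YF-AND 1.8 and YF-AVD 1.4 (age 60 and over). From section 3: 250 participants. Not in the documents: the share p of doses given at age 60 and over, which is varied below.

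**Step 1: reproduce the stated range.** The smaller and larger of the two syndrome rates are 0.4 and 0.8, an exact match. That the authors took them this way is an inference; the text does not say so.

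**Step 2: all-age totals, assuming no overlap between events.**
- Two syndromes: 0.8 + 0.4 = 1.2.
- With anaphylaxis: 1.2 + 1.8 = 3.0.
- Anaphylaxis against the stated upper end: 1.8 / 0.8 = 2.25.

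No all-age total falls within 0.4 to 0.8.

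**Step 3: allow for age.** If a fraction p of doses went to people aged 60 and over, the rate under 60 is (all-age rate − p × rate at 60+) / (1 − p). For the two syndromes together, the 60+ rate is 1.8 + 1.4 = 3.2, so the rate under 60 is (1.2 − 3.2p) / (1 − p).

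| Assumed p | YF-AND + YF-AVD under 60 | Room left for anaphylaxis below 0.8 |
|---|---|---|
| 0 | 1.20 | none |
| 0.10 | 0.98 | none |
| 1/6 | 0.80 | none |
| 0.20 | 0.70 | 0.10 |
| 0.25 | 0.53 | 0.27 |
| 0.286 | 0.40 | 0.40 |

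The last row is the largest possible p: at 0.4 / 1.4 = 0.286 the YF-AVD rate under 60 reaches zero. From p = 1/6 to p = 0.286 the two-syndrome total runs from 0.80 to 0.40, the stated range. So that range is possible for these two syndromes in people under 60, but the documents neither confirm nor refute it.

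For the range to hold with anaphylaxis included, serious anaphylaxis could be at most 0.4 / 1.8 = 22% of the listed rate at p = 0.286. If both syndromes were zero, the limit would be 0.8 / 1.8 = 44%. The allergy exclusion may lower the rate in this cohort, but no figure says by how much.

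**Step 4: what it means for this study.** The expected number of events is 250 × rate / 100,000, and the chance of at least one is 1 − exp(−expected number). Reporting rates are treated as probabilities here, for scale only.

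| Rate per 100,000 | Expected in 250 | Chance of at least one |
|---|---|---|
| 0.4 | 0.0010 | 0.10% |
| 0.8 | 0.0020 | 0.20% |
| 1.2 | 0.0030 | 0.30% |
| 3.0 | 0.0075 | 0.75% |

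**Step 5: where the figure is used.** Section 9 plans an exploratory, descriptive analysis and derives nothing from an SAE rate. The arm sizes in section 3, the criteria in section 4, the AE collection periods in section 7.2 and the reporting rules in section 7.5 do not refer to it.

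**The case for a change.** The strongest case for a correction is that the sentence gives a number, calls it overall and ties it to data in which one listed event alone is 2.25 times the upper end. Consulting experts does not help a reader who cannot see what they contributed. Lower syndrome rates in younger adults may rescue the range for the two syndromes, but they leave little or no room for anaphylaxis. One sentence would put it right.

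Much of this stands: as a total over all the listed events, the range is not supported, and the omission of anaphylaxis is not explained.

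Two parts do not stand. First, the range has not been shown to be wrong for what it most plausibly describes. The same section introduces severe events as specifically the two syndromes, and a two-syndrome total of 0.4 to 0.8 under age 60 is arithmetically possible. Second, 3.0 is no better as a figure for this cohort. It includes the higher rates from age 60, assumes no overlap, counts every anaphylaxis report as an SAE and ignores the allergy exclusion.

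Nor is anything hidden. The anaphylaxis rate is printed in the same paragraph, and participants are to read the Vaccine Information Sheet before vaccination (section 6.2). Anaphylaxis is also dealt with in practice, through the allergy exclusion and the observation period after injection.

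**Conclusion.** No change to the plan is needed. The word *overall* is a loose label on a background sentence that the authors present as their own judgement. Read as a statement about YF-AND and YF-AVD in younger adults, the range is possible though not demonstrated; read as a total including anaphylaxis, it is not supported.

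The size of any understatement at ages 18–45 cannot be fixed from the documents. That would need the age distribution of doses, an anaphylaxis rate for this age group and the effect of the allergy exclusion, and none is given. The age calculation rests on assumed values of p and uses under 60 as a stand-in for 18–45.

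The conclusion that the sentence supports does not depend on settling this. Between the lower end of the range and the all-age sum of 3.0, the chance of at least one such event among 250 participants goes from 0.10% to 0.75%, if passive reporting rates are taken as probabilities. Such rates are not incidences, so these percentages show scale only. Rewording the sentence would make it tidier, but it would alter nothing that the study does, measures or concludes.
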